### 14.4 Final Analyses

#### 14.4.1 Analysis of demographics

Demographic characteristics (age, gender and race) and health status characteristics (baseline CD4 counts, nadir CD4 T cell counts, pre-ART HIV-1 RNA levels, cART duration) will be tabulated by randomized treatment.

#### 14.4.2 Analysis of safety

For the safety analysis, AEs and SAEs will be recorded as described in this protocol and will be summarized in terms of frequency, severity and level of attribution to the study medication. Data will be reported as the

## Protocol

absolute and relative number of participants experiencing at least 1 event, the total number of events, the type of events, and the causality assessment. Due to the low expected safety event rates (based on the prior clinical study with panobinostat in HIV-1 participants), the study is not powered to do a formal statistical comparison between the randomized arms. AE rates will be presented for descriptive purposes.

### 14.4.3 Statistical analysis of virological and immunological data

The primary efficacy endpoint is the change from baseline to day 10 in the number of HIV-1 infected CD4 T cells, as assessed by proviral CD4 T cell-associated HIV-1 DNA levels determined on a log-scale. The null hypothesis of no difference in the primary efficacy endpoint between the randomized treatments will be tested using a one-sided Wilcoxon rank sum test. The null hypothesis will be rejected with a  $p < 0.05$ .

Changes in the frequency of HIV-1-infected CD4 T cells (determined by levels of CD4 T cell-associated proviral HIV-1 DNA) from baseline to completion of the treatment phase will also be summarized as secondary efficacy endpoints and compared between the two randomized treatments. Mean and quartile plots will be used to summarize these efficacy endpoints at each visit. If feasible with the modest sample size, longitudinal data methods will also be used to evaluate and estimate treatment effects.

Analysis for the primary efficacy endpoint will use a modified intent-to-treat analysis, limiting to participants who have received at least one dose of randomized treatment and have data at baseline and day 10. Participants who go off ART, experience virologic failure or discontinue study participation for other reasons will be excluded from the efficacy analysis. For this analysis, mixed models with repeated measures will be considered (MMRM). Missing data will be managed using guidelines defined by the National Research Council.

Primary safety endpoints will be tabulated by Cohorts and randomized treatments.

Analyses of secondary virologic and immunologic outcomes will parallel the primary analyses outline above.

Baseline immunologic and virologic parameters will be assessed at multiple pre-entry timepoints (see Table 1). For analysis of primary and secondary endpoints, the mean of multiple baseline assessments will be used.

Secondary analyses of all immunologic and virologic parameters stratified by genetic polymorphisms (in HLA and IL-28B genes) will also be carried out.

Associations between changes in the various virologic and immunologic measurements will be evaluated using scatterplots and correlation coefficients.

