### 14.3 Sample Size Considerations

The primary efficacy analysis will compare changes from baseline to post-treatment HIV-1 DNA changes between the randomized treatment arms in stage 3. Allowing for one unevaluable participant in each arm due to lost to follow-up, ART discontinuation and/or other reasons, and under the assumption that a common standard deviation of change (measured as difference of log10 transformed HIV-1 DNA copies/million CD4 T cells) in all treatment arms is 0.436 (derived from baseline to end-of-study change in

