## Protocol

the CLEAR study), the study with N=18 participants (9 evaluable participants treated with panobinostat and PEG-IFN- $\alpha$ 2a and 3 each treated with panobinostat or PEG-IFN- $\alpha$ 2a alone) will have 80% power to detect an effect size of 0.82  $\log_{10}$  (6.6-fold) in change of proviral CD4 T cell-associated HIV DNA level from baseline to day 10 in participants treated with panobinostat and PEG-IFN- $\alpha$ 2a compared to participants treated with panobinostat or PEG-IFN- $\alpha$ 2a only using a one-sided Wilcoxon rank sum test on a level of  $\alpha=0.05$ , assuming a normal distribution. The above power estimation does not take into account of multiple comparisons for this pilot study.

True Probability	N =8	N =8
	Probability of at least 1 event	Probability of at least 2 events
0.01	0.08	0.00
0.05	0.34	0.06
0.10	0.57	0.19
0.12	0.64	0.25
0.15	0.73	0.34
0.20	0.83	0.50

**Table 7:** Probability of safety endpoints in stage 1 and 2.

Regarding the assessment of safety, Table 7 and Table 8 display the probability of observing at least one or two participants with primary safety event with n=8 and 18 receiving study treatment. If the true probability is 10%, the study will have >57% probability of observing at least one participant with primary safety event in Stage 1 and 2 with 8 participants. The probability will be 85% for Stage 3 with N=18 participants.

True Probability	N =18	N =18
	Probability of at least 1 event	Probability of at least 2 events
0.01	0.17	0.01
0.05	0.60	0.23
0.10	0.85	0.55
0.12	0.90	0.65
0.15	0.95	0.78
0.20	0.98	0.90

**Table 8:** Probability of safety endpoints in stage 3.

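### At 9 versus 3 evaluable, the primary rank-sum test as written has about 72% power with exact p-values, not 80%, and uses baseline HIV-1 DNA only by subtraction; an exact baseline-adjusted permutation test should be pre-specified

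*Combined protocol and SAP*

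**What the plan says.** Section 14.4.3 defines the primary efficacy endpoint as the change from baseline to day 10 in log HIV-1 DNA. The null hypothesis of no difference between arms "will be tested using a one-sided Wilcoxon rank sum test". The decision rule ("The null hypothesis will be rejected with a" p below 0.05) is a strict inequality. For baseline, "the mean of multiple baseline assessments will be used"; Table 1 schedules HIV-1 DNA twice before dosing, at V2 and at day 0. The section adds that mixed models will be considered, but names no covariate.

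Section 14.3 plans on "the study with N=18 participants (9 evaluable participants treated with panobinostat and PEG-IFN"-α2a, with 3 in each single-drug arm. It claims that the study "will have 80% power to detect an effect size of 0.82" log10, "using a one-sided Wilcoxon rank sum test on a level of" 0.05, "assuming a normal distribution". The SD of change "in all treatment arms is 0.436 (derived from baseline to end-of-study change in" the earlier single-group panobinostat study). Neither section says whether the p-value is exact or approximate, and neither gives a correlation between baseline and change.

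**The concern.** Two features of the primary test cost information when a comparison has three controls.

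- **Coarseness.** The rank-sum statistic takes few values near the 5% level. Whether the boundary value counts as rejection therefore changes both the true level and the power. The power statement and the decision rule appear to assume different answers.
- **Baseline.** A change score fixes the slope of day 10 on baseline at 1. If the true slope is lower, change still depends on baseline, and part of a chance imbalance carries into the arm difference. Imbalance is likely with 3 or 4 controls. Both early and chronic ART starters are eligible (section 7.1.6), and section 7.5 describes no stratification.

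At stake is whether the only formal efficacy test delivers its stated power, and whether data already being collected could improve it without extra participants.

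**Working it through.** **Inputs.** From section 14.3: 9 vs 3 evaluable, SD of change 0.436, difference 0.82 log10 (10^0.82 = 6.6-fold), one-sided 0.05, normal data. From section 14.4.3: strict p < 0.05. Assumed: the baseline-change correlation r.

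**1. The plan's own figure.** There are C(12,3) = 220 equally likely allocations under the null. Cumulative counts for the Mann-Whitney U are:

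| U at most | Allocations | Exact one-sided p |
|---|---|---|
| 2 | 4 | 0.018 |
| 3 | 7 | 0.032 |
| 4 | 11 | 0.0500 |
| 5 | 16 | 0.073 |

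In simulation (40,000 trials per setting), rejecting at U ≤ 4 gives 80% power, which reproduces the stated figure. Pooling the two single-drug arms (9 vs 6) would give about 95-97% by t and z approximations, so the 80% refers to 9 vs 3.

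**2. The rule as written.** An exact p of 11/220 = 0.0500 is not below 0.05, so rejection needs U ≤ 3. The level is 7/220 = 3.2% and the simulated power about 72%.

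**3. Baseline-adjusted permutation test.** Regress change on arm and mean baseline, take the t-statistic for arm, and compare it with its values over all 220 re-allocations. Attainable levels are 10/220 = 4.5% (strict) and 11/220 = 5.0%. Simulated type I error was 4.4-4.6% and 4.9-5.1%.

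Power depends on r. With equal SDs at baseline and day 10 and baseline to day-10 correlation ρ, r = -√((1-ρ)/2); for example, ρ = 0.5 gives -√0.25 = -0.5. Power in % with the SD of change held at 0.436:

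| ρ | r | Rank-sum, p<0.05 | Adjusted perm., p<0.05 | Unadjusted perm., p<0.05 | Rank-sum, p≤0.05 | Adjusted perm., p≤0.05 | Unadjusted perm., p≤0.05 |
|---|---|---|---|---|---|---|---|
| 0 | -0.71 | 71.7 | 95.4 | 81.3 | 79.7 | 96.0 | 82.9 |
| 0.5 | -0.50 | 71.6 | 86.2 | 81.0 | 80.1 | 87.6 | 82.6 |
| 0.7 | -0.39 | 71.6 | 82.3 | 81.3 | 79.8 | 83.8 | 82.9 |
| 0.8 | -0.32 | 72.1 | 80.8 | 81.5 | 80.3 | 82.4 | 83.1 |
| 0.9 | -0.22 | 72.1 | 78.8 | 81.4 | 80.2 | 80.6 | 83.0 |
| 0.95 | -0.16 | 71.9 | 77.6 | 81.1 | 80.0 | 79.4 | 82.7 |

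Separate runs set directly by r gave the adjusted test 77% at r = 0 and 78% at r = -0.2 under strict p < 0.05. With p ≤ 0.05 for both tests, it had 79% against 79-80% for the rank-sum at those two values.

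**4. Which r is plausible?** As an illustration, suppose that change reflects only independent measurement error with variance σ² per draw, and that baseline is the mean of two draws. Then 1.5σ² = 0.436² = 0.190, so σ² = 0.127. With between-person SD s, r = -(σ²/2)/√((s² + σ²/2)·1.5σ²).

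- s = 0: r = -0.58, the strongest value possible.
- s = 0.3: r = -0.063/√(0.153 × 0.190) = -0.37.
- s = 0.7: r = -0.063/√(0.553 × 0.190) = -0.20.

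Under this mechanism -0.7 cannot occur, and -0.5 needs s of only about 0.15.

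**The case against.** The strongest reply is that the planned test is valid and its 80% reproduces. The 72% appears only if an exact p of 0.0500 is held to fail a strict inequality, and changing one symbol restores 80%. That is fair. The plan also does not say that p-values are exact: the usual normal approximation gives U = 4 a p of 0.048 with continuity correction (0.040 without), which rejects. So the documents do not show that 80% is wrong. They show that the decision rule leaves open whether it is attained.

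A second reply is that much of the gain has nothing to do with baseline. This also stands. An unadjusted exact permutation test of mean change has about 81% power at strict p < 0.05 whatever r is, and it beats the adjusted test until r reaches about -0.3 to -0.4. Estimating a slope with three controls costs precision.

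Two stronger readings are tempting, and neither is supported.

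- **That the test ignores baseline.** It does not: the mean of two pre-dose values is subtracted, and averaging already dampens regression to the mean.
- **That adjustment raises power whatever the data look like.** Over the written strict rule it gains at every r examined. Over a p ≤ 0.05 rank-sum it roughly ties for r from 0 to -0.2 and gains from about -0.3. The documents give no r. Nor do they say that HIV-1 DNA differs between early and chronic starters; greater between-person spread would in fact weaken r.

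**Conclusion.** The point holds in a limited form. Read literally with exact p-values, the primary test at 9 vs 3 runs at 3.2% with about 72% power, 8 points below the stated 80%. The exact baseline-adjusted permutation test keeps its level and beats that literal rule at every correlation examined: about 77%, 81%, 86% and 95% at r = 0, -0.3, -0.5 and -0.7. Against a rank-sum that rejects at p ≤ 0.05, the benefit is modest over the range that measurement error would suggest: about 0 to 4 points for r between -0.2 and -0.4.

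These figures assume normal data, an additive effect, an SD of change of 0.436 and exactly 9 vs 3 evaluable. The table also assumes equal SDs at the two times. If nobody is lost (10 vs 4), no rank-sum p-value falls on 0.05: the level is 38/1001 = 3.8% under either inequality, since the next value is 53/1001 = 0.053. A permutation test could then use 50/1001 = 4.995%.

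**What to change.** Before any stage 3 data are seen:

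1. In section 14.4.3, state that p-values are exact and that exact p ≤ 0.05 rejects. Otherwise, restate the power in section 14.3 as about 72%.
2. For B vs A and for B vs C, pre-specify a one-sided exact permutation test over all re-allocations of the difference in day-10 log10 HIV-1 DNA change, adjusted for mean baseline log10 HIV-1 DNA. Make it the primary analysis or, at minimum, the key supportive one. Report the adjusted difference with its interval alongside the rank-sum result.
3. Settle the covariate in advance from stage 1-2 data or the earlier panobinostat study. If r looks weaker than about -0.3, the unadjusted permutation test of mean change is the better choice. Stages 1-2 alone will not fix r: with 16 participants, an observed -0.3 has an approximate 95% interval of tanh(-0.31 ± 1.96/√13), or -0.69 to 0.23. The sources should be used together and the choice recorded.

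This costs SAP wording and a few lines of code, with no new data or visits. The downside is up to about 4 points of power relative to the unadjusted permutation test (77% vs 81%) if baseline and change prove uncorrelated.

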## 15.0 DATA MANAGEMENT

### 15.1 Data Management

All study patient visits will be documented by the study nurses and physicians on case report forms provided by the sponsor. A study data manager will be responsible for storing these patient-related data in paper or electronic form at a central repository in the hospital.

### 15.2 Confidentiality

Data on participants enrolled will be coded with a non-identifiable number. Access to confidential data such as participant identifiers and specific demographic data will be restricted to only those research team members for whom access is necessary, as defined by the study sponsor.

## Protocol

### **16.0 PUBLICATION OF RESEARCH FINDINGS**

Publication of the results of this trial will be governed by requirements for authorship promulgated by the International Committee of Medical Journal Editors (ICMJE), which have been adopted by many biomedical journals and are posted on its website at <http://www.icmje.org>. Any presentation, abstract, or manuscript will be made available for review by the pharmaceutical companies and DAIDS providing the investigational drugs at least thirty (30) days [or, for abstracts, at least five (5) working days] prior to submission.

### **17.0 BIOHAZARD CONTAINMENT**

As the transmission of HIV and other blood-borne pathogens can occur through contact with contaminated needles, blood, and blood products, appropriate blood and secretion precautions will be employed by all personnel in the drawing of blood and shipping and handling of all specimens for this study, as currently recommended by the Centers for Disease Control and Prevention and the NIH.

All infectious specimens will be transported using packaging mandated in the Code of Federal Regulations, CDC 42 CFR Part 72. Please also refer to individual carrier guidelines, e.g. FedEx, Airborne, for specific instructions.

### **18.0 PROTOCOL REGISTRATION**

#### **18.1 Introduction**

Prior to implementation of this protocol, and any subsequent full version amendments, the study site must have the protocol and the protocol informed consent form approved, as appropriate, by the local institutional review board (IRB)/ethics committee (EC) and any other applicable regulatory entity (RE). Upon receiving final approval, sites will submit all required protocol registration documents to the DAIDS Protocol Registration Office (DAIDS PRO) at the Regulatory Support Center (RSC). The DAIDS PRO will review the submitted protocol registration packet to ensure that all of the required documents have been received.

#### **18.2 Initial Registration**

Site-specific informed consent forms (ICFs) *WILL NOT* be reviewed or approved by the DAIDS PRO, and sites will receive an Initial Registration Notification when the DAIDS PRO receives a complete registration packet. Receipt of an Initial Registration Notification indicates successful completion of the protocol registration process. Sites will not receive any additional notifications from the DAIDS PRO for the initial protocol registration. A copy of the Initial Registration Notification should be retained in the site's regulatory files.

#### **18.3 Amendment Registration**

Upon receiving final IRB/EC and any other applicable RE approval(s) for an amendment, the study site should implement the amendment immediately. The study site is required to submit an amendment registration packet to the DAIDS PRO at the RSC. The DAIDS PRO will review the submitted protocol registration packet to ensure that all the required documents have been received. Site-specific ICF(s) *WILL NOT* be reviewed and approved by the DAIDS PRO and sites will receive an Amendment Registration Notification when the DAIDS PRO receives a complete registration packet. A copy of the Amendment Registration Notification should be retained in the site's regulatory files.

For additional information on the protocol registration process and specific documents required for initial and amendment registrations, refer to the current version of the DAIDS Protocol Registration Manual.

20.2 Novartis Safety Reporting Fax Cover Sheet

Protocol

**Protocol**

20.3 DAIDS Expedited Adverse Event Reporting Form (EAE form)

## Division of AIDS Safety Office EXPEDITED ADVERSE EVENT (EAE) Reporting Form

*Please type or print in English*

Why are you not using DAERS?

Reason for submitting report beyond the 3 reporting days (if applicable):

### REPORTER AND SITE INFORMATION

Site Name: 	Site ID: 
Site Awareness Date:  <small>DD/MON/YYYY</small>	Site Report Date:  <small>DD/MON/YYYY</small>
Reporter Same as Sender? YES  NO  <small>If YES, do not repeat contact information provided above.</small>	Reporter Name: 
	Phone:  Fax: 
	E-mail: 

### KEY EAE REPORT INFORMATION

Participant ID: 	Protocol No(s)/Version No(s): 
New Report:  <small>(Send all pages of the completed form.)</small>	Date of Initial Report:  <small>DD/MON/YYYY</small>
Update Report:  <small>(Provide date of original report.)</small>	
Pages:  1  2  3  4  5  6  7  8  ALL  OTHER  <small>(For Update Reports, submit only updated pages. Check all that apply.)</small>	

### ---- SAFETY OFFICE USE ONLY ----

Received Date Stamp:	
AE NUMBER: 	PROTOCOL NUMBER(S): 
Report Received By:  Fax  E-mail  Express Mail	

Protocol

Participant ID:

Site Report Date:   
DD/MON/YYYY

1. PARTICIPANT INFORMATION For each question below, please check the appropriate box.	
Date of Birth:  OR Age at time of event:   Days *  Months*  Years <small>DD/MON/YYYY * Pediatric Studies Only</small>	
Sex at Birth:  Male  Female  Unknown	Height:   cm  in
If Female, Pregnant?:  Yes  No  Unknown (If Yes) Duration:  week(s)	Weight:   kg  lb
Ethnicity:  Hispanic or Latino  Non-Hispanic or Latino  Unknown  Not Reported  Other 	Race:  American Indian or Alaska Native  Black or African American  White  Native Hawaiian or Other Pacific Islander  Asian  Not Reported  Unknown  Other 

**Protocol**

Participant ID:

Site Report Date:   
DD/MON/YYYY

2. PRIMARY ADVERSE EVENT				
Primary AE <small>List only one Primary AE</small>	Severity Grade of Primary AE*	Onset Date DD/MON/YYYY	Status Code**	Status Date DD/MON/YYYY
				
*Severity Grade of Primary AE: 1 – Mild 2 – Moderate 3 – Severe 4 – Life Threatening 5 – Death		**Status Code at Most Recent Observation: 1 – Recovered/Resolved 2 – Recovering/Resolving 3 – Not Recovered/Not Resolved 4 – Recovered/Recovered with Sequelae 5 – Death 6 – Unknown		

Country of AE Origin:

Is this a Serious Adverse Event (SAE) as defined by ICH* E2A? <small>(*International Conference on Harmonization)</small>	 YES  NO
If Yes, check all that apply: 
 
 Results in death
 
 Is life-threatening
 
 Requires inpatient hospitalization or prolongation of existing hospitalization
 
 Results in persistent or significant disability/incapacity
 
 Is a congenital anomaly/birth defect
 
 Is an important medical event that may not be immediately life-threatening or result in death or hospitalization but may jeopardize the patient or may require intervention to prevent one of the other outcomes listed in the definition above
 
	
If No, check applicable box: 
 
 None of the above – This is not an SAE, but is a protocol-specific reporting requirement
 
 None of the above – This is not an SAE, but is of sufficient concern to report to DAIDS.
 
 Comment(s): 	

**Protocol**

Participant ID:

Site Report Date:   
DD/MON/YYYY

3.	NARRATIVE CASE SUMMARY	Include clinical course, therapeutic measures, outcome, relevant past medical history, any other contributing factors, alternative etiologies, and other relevant information. Use additional page(s) as needed.
		

Protocol

Participant ID:

Site Report Date:   
DD/MON/YYYY

4a. FOR STUDY AGENTS OTHER THAN VACCINES OR THERAPEUTIC VACCINES							
For therapeutics administered on a cyclic schedule, also complete the Supplemental DAIDS EAE Report Form and check here  if attached.							
Protocol Number: (include information on co-enrolled protocols here)							
Study Agent:	Example	Agent 1	Agent 2	Agent 3	Agent 4	Agent 5	
Generic/INN Name: OR the Study Agent Name/Abbreviation as listed in the Protocol If combination agent, list as separate components separated by a slash.	Abacavir Sulfate/ Lamivudine/ Zidovudine						
Relationship to Primary AE*:	Related						
Provide relationship of each component when using a combination study agent. Refer to example and form completion instructions for details.	Abacavir = Related Lamivudine = Related Zidovudine = Not Related						
* Related — There is a reasonable possibility that the AE may be related to the study agent(s). Not Related — There is not a reasonable possibility that the AE may be related to the study agent(s).							
	Study Agent:		Agent 1	Agent 2	Agent 3	Agent 4	Agent 5
A	Dose/Unit/ Schedule:						
B	Route:						
C	Date of First Dose: DD/MON/YYYY						
D	Date of Last Dose: DD/MON/YYYY						
E	Action Taken with Study Agent**:						
F	Date of Action Taken With Study Agent: DD/MON/YYYY						
G	Distributed by DAIDS:	Yes  No 	Yes  No 	Yes  No 	Yes  No 	Yes  No 	Yes  No 
	If No, specify manufacturer. If unknown, specify distributor.						
H	Lot No:						
**	C Continued without change	O Course completed or Subject Off Study Agent at AE Onset	D Permanently Discontinued	R Dose or Schedule Reduced	T Temporarily Held	U Unknown	

**Protocol**

Participant ID:

Site Report Date:   
DD/MON/YYYY

4b. FOR VACCINES ONLY (INCLUDING THERAPEUTIC VACCINES)					
For therapeutics administered on a cyclic schedule, also complete the Supplemental DAIDS EAE Report Form and check here  if attached.					
Protocol Number: (include information on co-enrolled protocols here)					
Study Arm:					
Study Agent:	Agent 1	Agent 2	Agent 3	Agent 4	Agent 5
Generic/INN Name: OR the Study Agent Name/Abbreviation as listed in the Protocol					
Relationship to Primary AE*:					
* Related — There is a reasonable possibility that the AE may be related to the study agent(s). Not Related — There is not a reasonable possibility that the AE may be related to the study agent(s).					
Dose/Unit:					
Route:					
Device Lot Number: (if known/if applicable)					
List all dates (DD/MON/YYYY) of vaccine administration/agent(s) administered/site of administration					 N/A
A.  DD/MON/YYYY  Agent (s) Administered:   Site of Administration (if known/if applicable):  Left Arm  Right Arm  Left Leg  Right Leg  Other 	B.  DD/MON/YYYY  Agent(s) Administered:   Site of Administration (if known/if applicable):  Left Arm  Right Arm  Left Leg  Right Leg  Other 	C.  DD/MON/YYYY  Agent(s) Administered:   Site of Administration (if known/if applicable):  Left Arm  Right Arm  Left Leg  Right Leg  Other 	D.  DD/MON/YYYY  Agent(s) Administered:   Site of Administration (if known/if applicable):  Left Arm  Right Arm  Left Leg  Right Leg  Other 	E.  DD/MON/YYYY  Agent(s) Administered:   Site of Administration (if known/if applicable):  Left Arm  Right Arm  Left Leg  Right Leg  Other 	
Action Taken with Study Agent** (enter code for the vaccine treatment regimen from codes listed below): 				Date of Action Taken With Study Agent:  DD/MON/YYYY	
** C Continued without change	O Course completed or Subject Off Study Agent at AE Onset	D Permanently Discontinued	R Dose or Schedule Reduced	T Temporarily Held	U Unknown

